10.3.2 Definition of SAE

An SAE is defined as any untoward medical occurrence that, at any dose, meets one or more of the criteria listed:

a) Results in death

b) Is life-threatening

The term *life-threatening* in the definition of *serious* refers to an event in which the participant was at risk of death at the time of the event. It does not refer to an event, which hypothetically might have caused death, if it were more severe.

c) Requires inpatient hospitalization or prolongation of existing hospitalization

In general, hospitalization signifies that the participant has been admitted (usually involving at least an overnight stay) at the hospital or emergency ward for observation and/or treatment that would not have been appropriate in the physician's office or outpatient setting. Complications that occur during hospitalization are AEs. If a complication prolongs hospitalization or fulfills any other serious criteria, the event is serious. When in doubt as to whether hospitalization occurred or was necessary, the AE should be considered serious.

Hospitalization for elective treatment of a pre-existing condition that did not worsen from baseline is not considered an AE.

d) Results in persistent or significant disability/incapacity

- The term disability means a substantial disruption of a person's ability to conduct normal life functions,
- This definition is not intended to include experiences of relatively minor medical significance such as uncomplicated headache, nausea, vomiting, diarrhea, influenza, and accidental trauma (eg, sprained ankle) that may interfere with or prevent everyday life functions but do not constitute a substantial disruption.

e) Is a congenital anomaly/birth defect

f) Is a suspected transmission of any infectious agent via an authorized medicinal product

g) Other situations:

- Medical or scientific judgment should be exercised by the Investigator in deciding whether SAE reporting is appropriate in other situations such as significant medical events that may jeopardize the participant or may require medical or surgical intervention to prevent one of the other outcomes listed in the above definition. These events should usually be considered serious,

- Note: The following list of medically important events is intended to serve as a guideline for determining which condition has to be considered as a medically important event. The list is not intended to be exhaustive:
 - Intensive treatment in an emergency room or at home for:
 - Allergic bronchospasm,
 - Blood dyscrasias (ie, agranulocytosis, aplastic anemia, bone marrow aplasia, myelodysplasia, pancytopenia, etc),
 - Convulsions (seizures, epilepsy, epileptic fit, absence, etc).
 - Development of drug dependence or drug abuse,
 - ALT >3 × ULN + total bilirubin >2 × ULN or asymptomatic ALT increase >10 × ULN,
 - Suicide attempt or any event suggestive of suicidality,
 - Syncope, loss of consciousness (except if documented as a consequence of blood sampling),
 - Bullous cutaneous eruptions.

10.3.3 Recording and follow-up of AE and/or SAE

AE and SAE recording

- When an AE/SAE occurs, it is the responsibility of the Investigator to review all documentation (eg, hospital progress notes, laboratory reports, and diagnostics reports) related to the event.
- The Investigator will then record all relevant AE/SAE information.
- It is **not** acceptable for the Investigator to send photocopies of the participant's medical records to the Sponsor's representative in lieu of completion of the required form.
- There may be instances when copies of medical records for certain cases are requested by the Sponsor's representative. In this case, all participant identifiers, with the exception of the participant number, will be redacted on the copies of the medical records before submission to the Sponsor's representative.
- The Investigator will attempt to establish a diagnosis of the event based on signs, symptoms, and/or other clinical information. Whenever possible, the diagnosis (not the individual signs/symptoms) will be documented as the AE/SAE.

Assessment of intensity

The Investigator will make an assessment of intensity for each AE and SAE reported during the study and assign it to one of the following categories according to NCI-CTCAE v5.0.

• Mild: Asymptomatic or mild symptoms; clinical or diagnostic observations only; intervention not indicated.

- Moderate: Minimal, local or noninvasive intervention indicated; limiting age-appropriate instrumental Activities of Daily Living (ADL). Instrumental ADL refers to preparing meals, shopping for groceries or clothes, using the telephone, managing money, etc.
- Severe: Severe or medically significant but not immediately life-threatening; hospitalization or prolongation of hospitalization indicated; disabling, limiting self care ADL. Self care ADL refers to bathing, dressing and undressing, feeding self, using the toilet, taking medications, and not bedridden.

An event is defined as "serious" when it meets at least 1 of the pre-defined outcomes as described in the definition of an SAE, NOT when it is rated as severe.

Assessment of causality

- The Investigator is obligated to assess the relationship between study intervention and each occurrence of each AE/SAE. The Investigator will use clinical judgment to determine the relationship.
- A reasonable possibility of a relationship conveys that there are facts, evidence, and/or arguments to suggest a causal relationship, rather than that a relationship cannot be ruled out.
- Alternative causes, such as underlying disease(s), concomitant therapy, and other risk factors, as well as the temporal relationship of the event to study intervention administration will be considered and investigated.
- The Investigator will also consult the Investigator's Brochure (IB) and/or Product Information, for marketed products, in his/her assessment.
- For each AE/SAE, the Investigator must document in the medical notes that he/she has reviewed the AE/SAE and has provided an assessment of causality.
- There may be situations in which an SAE has occurred and the Investigator has minimal information to include in the initial report to the Sponsor. However, it is very important that the Investigator always make an assessment of causality for every event before the initial transmission of the SAE data to the monitoring team.
- The Investigator may change his/her opinion of causality in light of follow-up information and send an SAE follow-up report with the updated causality assessment.
- The causality assessment is one of the criteria used when determining regulatory reporting requirements.

Follow-up of AEs and SAEs

• The Investigator is obligated to perform or arrange for the conduct of supplemental measurements and/or evaluations as medically indicated or as requested by the Sponsor's representative to elucidate the nature and/or causality of the AE or SAE as fully as possible. This may include additional laboratory tests or investigations, histopathological examinations, or consultation with other health care professionals.

- If a participant dies during participation in the study or during a recognized follow-up period, the Investigator will provide the Sponsor with a copy of any postmortem findings including histopathology.
- New or updated information will be recorded in the originally submitted documents.
- The Investigator will submit any updated SAE data to the Sponsor within 24 hours of receipt of the information.

10.3.4 Reporting of SAEs

SAE reporting to the Sponsor via an electronic data collection tool

- The primary mechanism for reporting an SAE to the Sponsor's representative will be the electronic data collection tool.
- If the electronic system is unavailable, then the site will use the paper SAE data collection tool (see next section) to report the event within 24 hours.
- The site will enter the SAE data into the electronic system as soon as it becomes available.
- After the study is completed at a given site, the electronic data collection tool will be taken offline to prevent the entry of new data or changes to existing data.
- If a site receives a report of a new SAE from a study participant or receives updated data on a previously reported SAE after the electronic data collection tool has been taken offline, then the site can report this information on a paper SAE form (see next section) or to the Sponsor's representative by telephone.
- Contacts for SAE reporting can be found in in the Investigator study file.

SAE reporting to the Sponsor via paper data collection tool

- Facsimile transmission of the SAE paper data collection tool is the preferred method to transmit this information to the Sponsor's representative.
- In rare circumstances and in the absence of facsimile equipment, notification by telephone is acceptable with a copy of the SAE data collection tool sent by overnight mail or courier service.
- Initial notification via telephone does not replace the need for the Investigator to complete and sign the SAE data collection tool within the designated reporting timeframes.
- Contacts for SAE reporting can be found in in the Investigator study file.

10.4 APPENDIX 4: CONTRACEPTIVE AND BARRIER GUIDANCE

10.4.1 Definitions

A woman is considered WOCBP (fertile) from the time of menarche until becoming postmenopausal (see below) unless permanently sterile (see below).

- A postmenopausal state is defined as the period of time after a woman has experienced no menses for 12 consecutive months without an alternative medical cause.
- A high follicle-stimulating hormone (FSH) level in the postmenopausal range may be used to confirm a postmenopausal state in women not using hormonal contraception or HRT.
- Females on HRT and whose menopausal status is in doubt will be required to use one of the non-estrogen hormonal highly effective contraception methods if they wish to continue their HRT during the study. Otherwise, they must discontinue HRT to allow confirmation of postmenopausal status before study enrollment.

Permanent sterilization methods include:

- Documented hysterectomy.
- Documented bilateral salpingectomy.
- Documented bilateral oophorectomy.
- For individuals with permanent infertility due to an alternate medical cause other than the above, (eg, Mullerian agenesis, androgen insensitivity, gonadal dysgenesis), Investigator discretion should be applied to determining study entry eligibility.

Note: Documentation can come from the site personnel's review of the participant's medical records, medical examination, or medical history interview.

If fertility is unclear (eg, amenorrhea in adolescents or athletes) and a menstrual cycle cannot be confirmed before first administration of study intervention, additional evaluation should be considered.

10.4.2 Contraception guidance

CONTRACEPTIVES^a ALLOWED DURING THE STUDY INCLUDE:

Highly Effective Methods^b **That Have Low User Dependency** *Failure rate of <1% per year when used consistently and correctly.*

- Implantable progestogen-only hormone contraception associated with inhibition of ovulation^c
- Intrauterine device (IUD)
- Intrauterine hormone-releasing system (IUS)^C
- Bilateral tubal occlusion
- Azoospermic partner (vasectomized or due to a medical cause)
 Azoospermia is a highly effective contraceptive method provided that the partner is the sole sexual partner of the woman of childbearing potential and the absence of sperm has been confirmed. If not, an additional highly effective method of

contraception should be used.

Note: documentation of azoospermia for a male participant can come from the site personnel's review of the participant's medical records, medical examination, or medical history interview.

Highly Effective Methods^b **That Are User Dependent** *Failure rate of <1% per year when used consistently and correctly.*

- Combined (estrogen- and progestogen-containing) hormonal contraception associated with inhibition of ovulation^c
 - oral
 - intravaginal
 - transdermal
 - injectable
- Progestogen-only hormone contraception associated with inhibition of ovulation^c
 - oral
 - injectable
- Sexual abstinence

Sexual abstinence is considered a highly effective method only if defined as refraining from heterosexual intercourse during the entire period of risk associated with the study intervention. The reliability of sexual abstinence needs to be evaluated in relation to the duration of the study and the preferred and usual lifestyle of the participant.

- a Contraceptive use by men or women should be consistent with local regulations regarding the use of contraceptive methods for those participating in clinical studies.
- *b* Failure rate of <1% per year when used consistently and correctly. Typical use failure rates differ from those when used consistently and correctly.
- *c* If locally required, in accordance with Clinical Trial Facilitation Group (CTFG) guidelines, acceptable contraceptive methods are limited to those which inhibit ovulation as the primary mode of action.

Note: Periodic abstinence (calendar, symptothermal, post-ovulation methods), withdrawal (coitus interruptus), spermicides only, and lactational amenorrhoea method (LAM) are not acceptable methods of contraception for this study. Male condom and female condom should not be used together (due to risk of failure with friction).

10.5 APPENDIX 5: GENETICS

Use/Analysis of DNA

- Genetic variation may impact a participant's response to study intervention, susceptibility to, and severity and progression of disease. Variable response to study intervention may be due to genetic determinants that impact drug absorption, distribution, metabolism, and excretion; mechanism of action of the drug; disease etiology; and/or molecular subtype of the disease being treated. Therefore, where local regulations and IRB/IEC allow, a blood sample will be collected for DNA/RNA analysis from consenting participants.
- DNA/RNA samples will be used for research related to tusamitamab ravtansine or non-squamous NSCLC and related diseases. They may also be used to develop tests/assays including diagnostic tests related to CEACAM5 targeting drug and NSQ NSCLC. Genetic research may consist of the analysis of one or more candidate genes or the analysis of genetic markers throughout the genome (as appropriate).
- DNA/RNA samples will be analyzed for determination of tumor mutation profile on plasma cfDNA and tumor DNA/RNA. Subtractive mutation analysis will be performed with germline DNA data to identify tumor-specific somatic genetic aberrations.

- The samples may be analyzed as part of a multi-study assessment of genetic factors involved in the response to tusamitamab ravtansine or study interventions of this class to understand study disease or related conditions.
- The results of genetic analyses may be reported in the clinical study report (CSR) or in a separate study summary.
- The Sponsor will store the DNA samples in a secure storage space with adequate measures to protect confidentiality.
- The samples will be retained while research on study intervention continues but no longer than 15 years or other period as per local requirements.

10.6 APPENDIX 6: RECOMMENDED SUPPORTIVE CARE AND/OR DOSE MODIFICATION GUIDELINES FOR DRUG-RELATED ADVERSE EVENTS

Event	Symptoms severity (NCI-CTCAE v5.0)	Dose modification	Supportive care guidelines
Infusion-related reaction	Grade 1-2 eg, Grade ≤2 nausea, headache, tachycardia, hypotension, rash, shortness of breath.	Interrupt SAR408701 infusion. SAR408701 may be resumed only after participant recovery, at half the previous infusion rate ^a .	Give diphenhydramine 50 mg IV and/or dexamethasone 10 mg IV. Dexamethasone can be added as premedication for upcoming cycles for SAR408701
	Grade 3-4 eg, symptomatic bronchospasm, urticaria lesions covering >30% BSA, hypotension, angioedema.	Interrupt SAR408701 infusion and definitively discontinue SAR408701.	Give diphenhydramine 50 mg IV and/or dexamethasone 10 mg IV and/or epinephrine and any required treatment per Investigator judgment.
Ocular toxicity: Keratopathy/keratitis ^b associated with SAR408701	Grade 1 Asymptomatic, Corneal lesions only observed on routine ocular examination and not requiring topical treatment.	Next infusion of SAR408701 at the same dose, with or without cycle delay, depending on the recommendation from the ophthalmologist (nature and extent of the lesion).	Standard ocular examination is planned as recommended by the ophthalmologist.

Table 10 - Recommended Dose Modification or Discontinuation for SAR40870

Event	Symptoms severity (NCI-CTCAE v5.0)	Dose modification	Supportive care guidelines
	Grade 2 Symptomatic, moderate decrease in visual acuity (best corrected visual acuity 20/40 and better or 3 lines or less decreased vision from known baseline)	1 st episode: SAR408701 cycle delay until resolution to Grade 1 (asymptomatic) and restart SAR408701 at the same dose. 2 nd episode: delay cycle until resolution to Grade 1 (asymptomatic) and SAR408701 dose reduction.	Standard ocular examination weekly until resolution ^{c} . Start curative treatment per ophthalmologist recommendation. After resuming study treatment, participant should be followed with standard ocular examination by every 2 cycles, even asymptomatic during next four cycles. If no recurrence, standard process with follow-up with ocular symptom is resumed. Management of study drug and follow-up process upon recurrence
	Grade 3 Symptomatic with marked decrease in visual acuity (best corrected visual acuity worse than 20/40 or more than 3 lines of decreased vision from known baseline, up to 20/200); corneal ulcer; limiting self-care ADL.	1 st episode: SAR408701 cycle delay until resolution (asymptomatic) and restart SAR408701 with dose reduction. 2 nd episode: definitive discontinuation of SAR408701.	to be discussed according to Grade of the event at recurrence, clinical benefit from study drug and recommendation from the ophthalmologist.
	Grade 4 Perforation, best corrected visual acuity of 20/200 or worse in the affected eye	Definitive discontinuation of SAR408701.	Complete the corneal examination as recommended by ophthalmologist. Repeat the standard ocular examination weekly ^c until resolution. Start curative treatment per ophthalmologist recommendation.
Conduction disorder associated with SAR408701	Grade 1 Mild symptoms	SAR408701 administration to be continued upon decision by the Investigator and Sponsor, depending on the nature of the conduction disorder.	ECG performed once weekly until event resolution. Additional evaluations such as LVEF and Holter monitoring should be performed when relevant.
	Grade ≥2	Definitive discontinuation of SAR408701.	ECG to be repeated twice weekly until event resolution. Prompt cardiology consultation Additional evaluations such as LVEF and Holter monitoring should be performed when relevant.
Neutrophil count decreased	Grade 1 <lln-1500 mm³;
<lln-1.5 109/L</lln-1.5></lln-1500>	No change in IMPs administration.	No intervention.

Event	Symptoms severity (NCI-CTCAE v5.0)	Dose modification	Supportive care guidelines
	Grade 2 <1500-1000/mm³; <1.5-1.0 × 10 ⁹ /L	Delay the cycle until recovery of ANC >1500/mm ³ . Restart at the same dose.	No intervention.
	Grade 3 <1000-500/mm ³ ; <1.0-0.5 × 10 ⁹ /L Or Grade 4 <500/mm ³ ; <0.5 × 10 ⁹ /L	Delay the cycle. Restart the treatment when ANC >1500/mm ³ at the same dose. Prophylactic G-CSF can be considered in all subsequent cycles	Follow ASCO guidelines on usage G-CSF and antibiotherapy (20). Repeat the test every 3 days.
	Grade 4 >7 days <500/mm ³ ; <0.5 × 10 ⁹ /L	Delay the cycle until ANC >1500/mm ³ . 1st episode: administer next cycle at the same dose and administer growth factors 2nd episode: administer SAR408701 at reduced dose 3rd episode: definitive discontinuation	Follow ASCO guidelines on usage G-CSF and antibiotherapy (20). Repeat the test every 3 days.
Febrile neutropenia	Grade 3 Absolute neutrophil count <1000/mm ³ with a single temperature of >38.3°C (101°F) or a sustained temperature of \geq 38°C (100.4°F) for more than 1 hour	Delay cycle until ANC >1500/mm ³ . 1st episode: administer next cycle at the same dose and administer G-CSF 2nd episode: administer SAR408701 at reduced dose 3rd episode: definitive discontinuation	To ensure relative dose intensity, G-CSF is recommended as secondary prophylaxis in all participants with Grade ≥3 febrile neutropenia ASCO guideline is recommended for supportive treatment if there are no defined clinical standards (20).
	Grade 4 Life-threatening consequences	Administration changes to be decided at the Investigator's discretion. 1st episode: administer next cycle at reduced dose and administer G-CSF or definitively discontinue 2nd episode: definitive discontinuation	
Hepatic enzyme increase	Grade 1-2	Administer SAR408701 as planned.	No intervention.
	Grade 3	Delay the cycle. Restart the treatment until recovery to Grade 1.	Additional liver function tests will be done every 2-3 days until recovery to baseline value.
	Grade 4	SAR408701 should be permanently discontinued.	Additional liver function tests will be done every 2-3 days until recovery to baseline value.
Peripheral neuropathy	Grade 1 Asymptomatic	No action	Participant who has ongoing grade 1 neuropathy has high risk of

Clinical Trial Protocol SAR408701-ACT17241 - tusamitamab ravtansine 27-Sep-2021 Version number: 1

Event	Symptoms severity (NCI-CTCAE v5.0)	Dose modification	Supportive care guidelines
	Grade 2 Moderate symptoms; limiting instrumental Activities of Daily Living	Delay cycle, dose reduction if no improvement with dose delay	worsening of his/her symptoms and should be closely followed.
	Grade 3 Severe symptoms; limiting self-care Activities of Daily Living	Definitive discontinuation	-
	Grade 4 Life-threatening consequences; urgent	Definitive discontinuation	-

ASCO = American Society of Clinical Oncology; BSA = Body surface area; ECG = Electrocardiogram; G-CSF = Granulocyte colony-stimulating factor; IMP = Investigational medicinal product; IV = Intravenous; LLN = Lower limit of normal; LVEF = Left ventricular ejection fraction; NCI-CTCAE = National Cancer Institute Common Terminology Criteria for Adverse Events; and RBC = Red blood cell.

- a SAR408701 is stable at least 7.5 hours in the infusion bag at room temperature. If necessary, a new infusion should be prepared with the remaining dose to be administered.
- b The NCI-CTCAE v5.0 grading is to be applied to keratopathy.
- c Standard ocular examination per protocol includes visual acuity, slit-lamp examination, Schirmer's test, and enquiring for ocular/visual symptoms.

10.7 APPENDIX 7: AES, ADES, SAES, SADES, USADES AND DEVICE DEFICIENCIES: DEFINITIONS AND PROCEDURES FOR RECORDING, EVALUATING, FOLLOW-UP, AND REPORTING IN MEDICAL DEVICE STUDIES

Not applicable.

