Prior/concomitant therapy

- E 11. Medical condition requiring concomitant administration of a medication with a narrow therapeutic window, that is metabolized by cytochrome P450 (CYP450) (see Appendix 11 [Section 10.11]), and for which a dose reduction cannot be considered.
- E 12. Medical conditions requiring concomitant administration of strong CYP3A inhibitor (see Appendix 11 [Section 10.11]), unless it can be discontinued at least 2 weeks before the first administration of study intervention.
- E 13. Concurrent treatment with any other anticancer therapy.
- E 14. Washout period before the first administration of study intervention of less than 3 weeks or less than 5 times the half-life, whichever is shorter, for prior anti-tumor therapy (chemotherapy, targeted agents, immunotherapy and radiotherapy, or any investigational treatment), if palliative radiotherapy washout period of less than 2 weeks.
- E 15. Any prior therapy targeting CEACAM5.
- E 16. Prior maytansinoid treatment (DM1 or DM4 anti-body drug conjugate [ADC]).

Prior/concurrent clinical study experience

E 17. Previous enrollment in this study, current participation in any other clinical study involving an investigational study treatment, or any other type of medical research.

Diagnostic assessments

E 18. Poor organ function as defined by any 1 of the following prior to IMP administration:

- a) Serum creatinine >1.5 × upper limit of normal (ULN) or estimated glomerular filtration rate (eGFR) <60 mL/min/1.73 m² as estimated using a Modification of Diet in Renal Disease (MDRD) formula.
- b) Total bilirubin >1.0 × ULN (excluding congenital conjugation disorders [Gilberts], for whom total bilirubin ≤3.0 × ULN, with direct bilirubin ≤1.5 × ULN, is allowed). or aspartate aminotransferase (AST), alanine aminotransferase (ALT) >2.5 × ULN (in case of documented liver metastasis, AST, ALT <5 × ULN is allowed).

- c) Neutrophils $<1.5 \times 10^{9}$ /L, platelet count $<100 \times 10^{9}$ /L, or hemoglobin <9 g/dL (blood infusion-free for at least 2 weeks).

Other exclusions

- E 19. Individuals accommodated in an institution because of regulatory or legal order; prisoners or participants who are legally institutionalized
- E 20. Any country-related specific regulation that would prevent the participant from entering the study see Appendix 8 (Section 10.8) of the protocol (country-specific requirements)

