6.5.1 Retreatment criteria

All participants entered into the study will be treated at Day 1. A participant may receive additional study interventions if he/she meets retreatment criteria as determined by the Investigator and agrees to be retreated. Throughout the study, study intervention will be unblinded.

On Day 1 of each subsequent cycle, the participant must meet all of the following criteria to be eligible for retreatment:

- Neutrophils count $\geq 1.5 \times 10^9$ /L.
- Platelets $\geq 100 \times 10^{9}$ /L.
- Total bilirubin $\leq 3.0 \times$ ULN, with direct bilirubin $\leq 1.5 \times$ ULN.
- AST, ALT $\leq 2.5 \times$ ULN or $\leq 5 \times$ ULN in case of documented liver metastasis.
- No IMP-related toxicity Grade >1 (except for alopecia) or baseline severity.

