7.1.3 Rechallenge

Reinitiation of intervention with the IMP will be done under close and appropriate clinical and/or laboratory monitoring once the Investigator will have considered according to his/her best medical judgment that the responsibility of the IMP(s) in the occurrence of the concerned AE was unlikely and if the selection criteria for the study are still met (refer to Section 6.5.1).

For a regional or national emergency declared by a governmental agency, contingency measures are included in Section 10.9 (Appendix 9: Contingency measures for a regional or national emergency that is declared by a governmental agency).

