8.2.6.6 Liver function tests

- Hepatic enzyme increase has been reported with tusamitamab ravtansine administration. Patients should be carefully followed and in case of Grade ≥3 abnormal liver function tests, additional liver function tests will be done every 2 to 3 days until recovery to baseline value. Tusamitamab ravtansine should be permanently discontinued in case of drug-induced Grade 4 liver enzyme increase.
- Grade \geq 3 (ie, >5 × ULN) increased liver enzyme events should be reported as AESIs.

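### Table 10's hepatic row permits dosing on Day 1 at liver enzyme levels that the mandatory retreatment criteria in Section 6.5.1 rule out

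*Protocol*

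**What the plan says.** **Hepatic enzymes, Table 10.** In Protocol Section 10.6 the row for Grade 1-2 hepatic enzyme increase reads "Administer SAR408701 as planned", with no supportive measure. The Grade 3 row delays the cycle until recovery to Grade 1, and the Grade 4 row stops the drug. The appendix is titled "RECOMMENDED SUPPORTIVE CARE AND/OR DOSE MODIFICATION GUIDELINES FOR DRUG-RELATED ADVERSE EVENTS".

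**Grade boundary.** Section 8.2.6.6 fixes the start of Grade 3 in its reporting rule: "ie, >5 × ULN) increased liver enzyme events should be reported as AESIs".

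**Retreatment gate.** Section 6.5.1 applies on Day 1 of each subsequent cycle: "the participant must meet all of the following criteria to be eligible for retreatment". Its list caps AST and ALT at 2.5 × ULN, or 5 × ULN with documented liver metastasis, and adds "No IMP-related toxicity Grade >1 (except for alopecia) or baseline severity". Section 7.1.3 uses the same gate for restarting treatment: "if the selection criteria for the study are still met (refer to Section 6.5.1".

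**Link between them.** Section 6.5 sends cycle delays and dose modifications for toxicity to Appendix 6. It bases adjustments on the worst grade within a cycle, and asks for the most conservative choice when several reactions lead to conflicting advice.

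**Infusion reactions.** Section 6.1 interrupts the infusion at Grade 2 or higher and permits half-rate resumption after recovery, with no upper grade. Table 10 permits resumption for Grade 1-2 and requires definitive discontinuation for Grade 3-4.

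**The concern.** A site managing a liver enzyme rise is sent by Section 6.5 to Table 10, where the Grade 1-2 row gives an unconditional instruction to dose. Neither that row nor Section 8.2.6.6 refers to Section 6.5.1. For some participants that instruction means dosing someone whom Section 6.5.1 makes ineligible for that cycle. Section 6.5 also urges sites to preserve the full regimen and dose intensity, which favours giving the infusion when the texts disagree.

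What is at stake is participant safety and uniform dosing across sites. Hepatotoxicity is a listed risk in Section 2.3.1, and liver enzyme rises of Grade 3 or higher are AESIs. SAP Section 3.6.1 tabulates cycle delays, so sites that follow different texts would also produce different delay counts. The primary analysis is not at stake.

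**Working it through.** There is no planned figure to reproduce. The check is a comparison of limits.

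**Inputs**
- Ceiling of the Table 10 Grade 1-2 row: 5 × ULN, because Section 8.2.6.6 starts Grade 3 above that value.
- Section 6.5.1 limit without liver metastasis: 2.5 × ULN. With documented liver metastasis: 5 × ULN.
- Section 6.5.1 toxicity line, read as requiring any IMP-related toxicity to be at Grade 1 or below, or back to baseline severity.

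**Ratio of ceilings (Table 10 ceiling / Section 6.5.1 limit)**
- Without liver metastasis: 5.0 / 2.5 = 2.0. The band of disagreement is above 2.5 and up to 5.0 × ULN.
- With liver metastasis: 5.0 / 5.0 = 1.0. There is no numeric disagreement.

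**Day 1 states, side by side**

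| State on Day 1 of a later cycle | Section 6.5.1 | Table 10 | Conflict |
|---|---|---|---|
| AST/ALT within the applicable limit; no IMP-related toxicity above Grade 1 or baseline | Eligible | Dose | No |
| Grade 2 earlier in the cycle, settled to the limits above by Day 1 | Eligible | Dose | No |
| (a) AST/ALT above 2.5 and up to 5 × ULN, no liver metastasis | Barred by the AST/ALT line | Dose | **Yes** |
| (b) IMP-related Grade 2 rise above baseline, with or without liver metastasis | Barred by the toxicity line | Dose | **Yes** |
| Grade 3 | Barred | Delay | No |

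Cases (a) and (b) can overlap. Appendix 6 is titled for drug-related events, so a rise judged unrelated arguably falls outside the row. Case (a) is stated by enzyme level because the numeric limit in Section 6.5.1 applies whatever the cause.

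**Which text is out of line.** Table 10 has five Grade 2 instructions apart from infusion reactions:
- Keratopathy, first episode: "SAR408701 cycle delay until resolution to Grade 1 (asymptomatic) and restart SAR408701 at the same dose".
- Conduction disorder: discontinue.
- Neutrophil count: delay until recovery.
- Peripheral neuropathy: delay, then reduce if there is no improvement.
- Hepatic enzymes: dose.

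So 1 of 5 doses without a delay or a stop. The Grade 3 hepatic row waits for Grade 1, so a rise falling from Grade 3 is held at Grade 2, whereas a rise that peaks at Grade 2 is dosed. The 2.5 × ULN limit is also the entry limit in exclusion criterion E 18: "alanine aminotransferase (ALT) >2.5 × ULN (in case of documented liver metastasis", where the higher allowance again depends on liver metastasis. These comparisons all point to the hepatic Grade 1-2 row.

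**Infusion reactions.** At Grade 3-4, Section 6.1 read alone permits resumption and Table 10 requires a stop. Section 6.1 is permissive, so a site that stops complies with both.

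**The case against.** The strongest reply is that the texts can be read together. Section 6.5.1 sits within Section 6.5 and makes every later infusion conditional on its criteria, so an infusion is only planned if the gate is passed. Table 10 was never a complete retreatment rule, since Section 6.5.1 sets platelet and bilirubin limits that have no row in the table. Timing also differs: Table 10 responds to the worst grade in the cycle, and the gate to the state on Day 1.

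Much of this stands. It makes Section 6.5.1 the controlling text, gives a careful site a definite answer, and limits the conflict to rises still present on Day 1. It does not make the row right. The condition is not written there, and the table states a delay or a stop at Grade 2 for every other non-infusion event. The most-conservative clause in Section 6.5 does not settle the matter either, because it covers several reactions rather than two rules for one reaction.

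A reader might infer that every Grade 1-2 rise is affected; the table of Day 1 states shows otherwise. A reader might also size the problem from the AST Grade 3-4 laboratory rates in Section 2.3.1. Those grades lie outside the band, and Table 10 already delays or stops there.

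On infusion reactions, a reader might infer that the protocol authorises re-exposure after Grade 3-4. It does not: Sections 6.5 and 8.2.6.1 send the site to Table 10, which requires discontinuation.

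**Conclusion.** The hepatic inconsistency is real and narrow. It exists only on Day 1 of a later cycle, in cases (a) and (b). Without liver metastasis the row reaches twice the mandatory limit; with liver metastasis only the related-toxicity line is breached. A site that withholds departs only from a recommendation, whereas a site that follows the row doses against a mandatory criterion. The row is therefore the text to correct. That it is the drafting error is an inference from the rest of the table; no section states which text was intended.

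The conclusion rests on the 5 × ULN boundary in Section 8.2.6.6 and on the reading of the toxicity line given above. The documents report no rate of Grade 2 rises persisting on Day 1, so neither a number of affected participants nor a probability of misdosing can be supported. ORR, the interim rule and the sample size are unaffected. The point should be fixed on dosing-safety grounds. The infusion-reaction wording is a secondary alignment point.

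**What to change.** **Table 10, hepatic enzyme increase, Grade 1-2:** replace the instruction with *Administer at the same dose if the Section 6.5.1 retreatment criteria are met on Day 1; otherwise delay the cycle until they are met.*

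**Section 6.1, infusion reactions (secondary):** limit half-rate resumption to reactions of Grade 2 or lower, and refer to Table 10 for definitive discontinuation at Grade 3-4.

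**Cost:** a clarifying protocol amendment, with whatever ethics committee or health authority approval Section 10.1.1 requires, and notification of sites. A few cycles that a site would have given on the row alone may be delayed. Tumor assessments are timed from Cycle 1 Day 1 and do not move with cycle delays (Section 8.1), so the response schedule is unchanged. No procedure is added and no analysis changes.
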